## 5.7 Criteria for Removal from the Study

Treatment with study drugs is to be discontinued when any of the following occurs:

- Lack of therapeutic effect (any effort should be made to provide therapy to the patient in a safe way for at least 3-6 cycles for proper assessment of potential efficacy)
- Adverse event(s) that, in the judgment of the Investigator, may cause severe or permanent harm or which rule out continuation of study drug.
- Withdrawal of consent
- Lost to follow up
- Death
- Suspected pregnancy

## 6.0 CRITERIA FOR RESPONSE

Best overall response will be categorized according to the International Working Group Criteria (for all response categories, benefit must last at least for 12 weeks to qualify as a response) :

**Complete remission (CR):** Requires all of the following in the absence of both transfusion and growth factor support:

- Bone marrow: Age-adjusted normocellularity; <5% blasts;  $\leq$ grade 1 MF† and
- Peripheral blood: Hemoglobin  $\geq$ 10 g/dL and <UNL; neutrophil count  $\geq$   $1.0 \times 10^9/L$  and <UNL;
- Platelet count  $\geq$ 100  $\times$   $10^9/L$  and <UNL; <2% immature myeloid cells‡ and
- Clinical: Resolution of disease symptoms; spleen and liver not palpable; no evidence of EMH

**Partial remission (PR):**

- Peripheral blood: Hemoglobin  $\geq$ 10 g/dL and <UNL; neutrophil count  $\geq$   $1 \times 10^9/L$  and <UNL; platelet count  $\geq$ 100  $\times$   $10^9/L$  and <UNL; <2% immature myeloid cells and
- Clinical: Resolution of disease symptoms; spleen and liver not palpable; no evidence of EMH or
- Bone marrow: Age-adjusted normocellularity; <5% blasts;  $\leq$ grade 1 MF†, and peripheral blood: Hemoglobin  $\geq$ 8.5 but <10 g/dL and <UNL; neutrophil count  $\geq$   $1 \times 10^9/L$  and <UNL; platelet count  $\geq$ 50, but <100  $\times$   $10^9/L$  and <UNL; <2% immature myeloid cells‡ and
- Clinical: Resolution of disease symptoms; spleen and liver not palpable; no evidence of EMH

**Clinical improvement (CI):** The achievement of anemia, spleen or symptoms response without progressive disease or increase in severity of anemia, thrombocytopenia, or neutropenia§

Anemia response	Transfusion-independent patients: a $\geq$ 2.0 g/dL increase in hemoglobin level  Transfusion-dependent patients: becoming transfusion-independent ¶
Spleen response #	A baseline splenomegaly that is palpable at 5-10 cm, below the LCM, becomes not palpable or A baseline splenomegaly that is palpable at >10 cm, below the LCM, decreases by $\geq$ 50% A baseline splenomegaly that is palpable at <5 cm, below the LCM, is not eligible for spleen response
Symptoms response	A $\geq$ 50% reduction in the MPN-SAF TSS ††

**Progressive disease:**

- Appearance of a new splenomegaly that is palpable at least 5 cm below the LCM or
- A  $\geq$ 100% increase in palpable distance, below LCM, for baseline splenomegaly of 5-10 cm or
- A 50% increase in palpable distance, below LCM, for baseline splenomegaly of >10 cm or

- Leukemic transformation confirmed by a bone marrow blast count of  $\geq 20\%$  or
- A peripheral blood blast content of  $\geq 20\%$  associated with an absolute blast count of  $\geq 1 \times 10(9)/L$  that lasts for at least 2 weeks

**Stable disease:** Belonging to none of the above listed response categories

**Relapse:**

- No longer meeting criteria for at least CI after achieving CR, PR, or CI, or
- Loss of anemia response persisting for at least 1 month or
- Loss of spleen response persisting for at least 1 month
- Recommendations for assessing treatment-induced cytogenetic and molecular changes.

**Cytogenetic remission** At least 10 metaphases must be analyzed for cytogenetic response evaluation and requires confirmation by repeat testing within 6 months window  
CR: eradication of a preexisting abnormality  
PR:  $\geq 50\%$  reduction in abnormal metaphases  
(partial response applies only to patients with at least ten abnormal metaphases at baseline)

**Molecular remission** Molecular response evaluation must be analyzed in peripheral blood granulocytes and requires confirmation by repeat testing within 6 months window  
CR: Eradication of a pre-existing abnormality  
PR:  $\geq 50\%$  decrease in allele burden  
(partial response applies only to patients with at least 20% mutant allele burden at baseline)

**Cytogenetic/molecular relapse** Re-emergence of a pre-existing cytogenetic or molecular abnormality that is confirmed by repeat testing

*EMH, extramedullary hematopoiesis (no evidence of EMH implies the absence of pathology- or imaging study-proven nonhepatosplenic EMH); LCM, left costal margin; UNL, upper normal limit.*

*\*Baseline and post treatment bone marrow slides are to be interpreted at one sitting by a central review process. Cytogenetic and molecular responses are not required for CR assignment.*

*†Grading of MF is according to the European classification: Thiele et al. European consensus on grading bone marrow fibrosis and assessment of cellularity. Haematologica.*

2005;90:1128. It is underscored that the consensus definition of a CR bone marrow is to be used only in those patients in which all other criteria are met, including resolution of leukoerythroblastosis. It should also be noted that it was a particularly difficult task for the working group to reach a consensus regarding what represents a complete histologic remission.

‡Immature myeloid cells constitute blasts + promyelocytes + myelocytes + metamyelocytes + nucleated red blood cells. In splenectomized patients, <5% immature myeloid cells is allowed.

§See above for definitions of anemia response, spleen response, and progressive disease. Increase in severity of anemia constitutes the occurrence of new transfusion dependency or a ≥20 g/L decrease in hemoglobin level from pretreatment baseline that lasts for at least 12 weeks. Increase in severity of thrombocytopenia or neutropenia is defined as a 2-grade decline, from pretreatment baseline, in platelet count or absolute neutrophil count, according to the Common Terminology Criteria for Adverse Events (CTCAE) version 4.0. In addition, assignment to CI requires a minimum platelet count of ≥25 000 × 10(9)/L and absolute neutrophil count of ≥0.5 × 10(9)/L.

¶Applicable only to patients with baseline hemoglobin of <100 g/L. In patients not meeting the strict criteria for transfusion dependency at the time of study enrollment (see as follows), but have received transfusions within the previous month, the pretransfusion hemoglobin level should be used as the baseline.

¶Transfusion dependency before study enrollment is defined as transfusions of at least 6 units of packed red blood cells (PRBC), in the 12 weeks prior to study enrollment, for a hemoglobin level of <85 g/L, in the absence of bleeding or treatment-induced anemia. In addition, the most recent transfusion episode must have occurred in the 28 days prior to study enrollment. Response in transfusion-dependent patients requires absence of any PRBC transfusions during any consecutive “rolling” 12-week interval during the treatment phase, capped by a hemoglobin level of ≥85 g/L.

#In splenectomized patients, palpable hepatomegaly is substituted with the same measurement strategy.

††Symptoms are evaluated by the MPN-SAF TSS. The MPN-SAF TSS is assessed by the patients themselves and this includes fatigue, concentration, early satiety, inactivity, night sweats, itching, bone pain, abdominal discomfort, weight loss, and fevers. Scoring is from 0 (absent/as good as it can be) to 10 (worst imaginable/as bad as it can be) for each item. The MPN-SAF TSS is the summation of all the individual scores (0-100 scale). Symptoms response requires ≥50% reduction in the MPN-SAF TSS.

‡‡Baseline values for physical examination refer to pretreatment baseline and not to post treatment measurements.

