### **Objectives**

Primary:

- to determine the efficacy of nivolumab as therapy for MF

Secondary:

- to determine the safety of nivolumab as therapy for patients with MF

Exploratory:

- to explore time to response and duration of response
- to assess changes in symptom burden
- to explore changes in bone marrow fibrosis
- to explore changes in JAK2V617F (or other molecular marker) allele burden or changes in cytogenetic abnormalities

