## 5.6 Evaluation During Study

- Directed history and physical examination including vital signs, body weight, and spleen and liver measurements on Days 1, 7, and 14 of Cycle 1, then on Day 1 and Day 14 (+/- 2 days) of Cycles 2 – 4, then on Day 1 of Cycle 5, and then on Day 1 (+/- 7 days) of every 3rd cycle after that (Cycles 8, 11, 14 and so on). This also includes a transfusion history and concomitant medication notation.
- CBC and differential, electrolytes (Na, K, Cl, HCO3), creatinine, BUN, glucose, total bilirubin, SGOT and SGPT, amylase and lipase on Days 1, 7, and 14 of Cycle 1, then on Day 1 and Day 14 of Cycles 2 – 4 (+/- 2 days), then on Day 1 of Cycle 5, and then on Day 1 (+/- 7 days) of every 3rd cycle after that (Cycles 8, 11, 14 and so on).
- Bone marrow aspiration and biopsy after 4 cycles, and if deemed appropriate by the investigator, then every 12 weeks.
- Response assessment after 4 cycles of therapy, then every 12 weeks
- Pregnancy test after 2 and 4 cycles of therapy, then every 12 weeks
- Continuous assessment of AEs
- MPN-SAF TSS questionnaire on Day 1 and Day 14 (+/- 2 days), of cycles 1-4, then on Day 1 of Cycle 5 (+/- 7 days), then Day 1 (+/- 7 days) of every 3rd cycle after that.

Every effort will be made to adhere to the schedule of events and all protocol requirements. Variations in schedule of events and other protocol requirements that do not affect the rights and safety of the patient will not be considered as deviations. Such variations may include laboratory and history and physical exam assessments completed outside of schedule, occasional missed required research samples.

The patient will be contacted by the PI and his staff approximately 30, 60 and 100 days after discontinuation of study drug to assess for AE's, unless the patient receives further MF-directed treatment. Pregnancy test (for FCBP only) will be required approximately 30, 60 and 100 days after discontinuation of study drug.

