## **9.0 STATISTICAL CONSIDERATIONS**

This is a single-center phase II trial to determine the efficacy of nivolumab as a monotherapy in subjects with Primary, Post Polycythemia Vera, or Post Essential Thrombocythemia Myelofibrosis (PMF, post-PV MF, or post-ET MF). The primary endpoint is the objective response rate (ORR) after 8 doses of therapy (4 cycles), defined as CR (complete remission) + PR (partial remission) + CI (clinical improvement). Responses will be categorized according to the revised International Working Group-Myeloproliferative Neoplasms Research and Treatment (IWG-MRT) and European LeukemiaNet (ELN) consensus criteria for myelofibrosis.

An optimum two-stage design proposed by Simon will be implemented. We assume a target ORR of 35%, and a response rate of 18% or lower will be considered not desirable. With a type I error rate of 7% and 80% power, we will enroll 16 patients in the first stage. If 3 or fewer patients achieve a response the trial will be stopped. If 4 or more out of the first 16 patients have a response, accrual will continue until a total of 40 patients have been enrolled. After the first 16 patients have enrolled, the study will not enroll new patient until enough responses (at least 4 responses out of 16 patients) are observed to warrant the continuation of the study. At the end of the study, if 11 or more out of these 40 patients achieve a response, the treatment of nivolumab will be considered efficacious and worth further investigation. Under this Simon's Optimum two-stage design, the probability of early termination is 68% if the true ORR is 18% and the expected sample size is 23.7 patients. Patients will be enrolled from MDACC and patients will be registered through the Clinical Oncology Research System (CORE). The estimated accrual rate is 1-2 patients per month. An interim analysis (response summary) will be submitted to the IND Monitor following the treatment of 16 and 40 patients.

The method of Thall, Simon and Estey will be used for toxicity monitoring for this study. Toxicity will be monitored among the 40 patients. Denote the probability of toxicity by  $p(T)$ ,

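### The central marrow read is not required to be masked to slide order or clinical response, which leaves fibrosis change and the marrow criteria for CR and PR open to expectation bias

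*Combined protocol and SAP*

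**What the plan says.** The reading method appears once, in the notes to the response criteria in Section 6.0: "Baseline and post treatment bone marrow slides are to be interpreted at one sitting by a central review process". Neither those notes, nor the evaluation schedule, nor Section 9.0 mentions coding of slides, order of reading, or what the reader may know about dates or clinical course.

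The readings are used in these places:

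- **Exploratory objective (Section 1.0):** "to explore changes in bone marrow fibrosis".
- **Complete remission (Section 6.0):** the marrow item begins "Bone marrow: Age-adjusted normocellularity; <5% blasts" and also asks for fibrosis of grade 1 or less.
- **Partial remission (Section 6.0):** there are two routes, and only the second has a marrow item.
- **Progressive disease (Section 6.0):** marrow blasts of 20% or more confirm leukemic transformation.

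Timing is set under Evaluation During Study: "Bone marrow aspiration and biopsy after 4 cycles, and if deemed appropriate by the investigator, then every 12 weeks". So there is one scheduled on-treatment marrow, and later ones are optional. Section 9.0 opens with "This is a single-center phase II trial"; there is one treatment group. The primary endpoint is the response rate after 4 cycles, "defined as CR (complete remission) + PR (partial remission) + CI (clinical improvement".

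**The concern.** Fibrosis grade and cellularity are matters of judgment. The notes to Section 6.0 themselves concede that the working group found complete histologic remission hard to define. A reader who knows which slide is later, or that the patient responded, may lean towards improvement when a grade is borderline. Reading both slides in one sitting controls drift between sessions but does nothing about expectation.

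There is no control group in which the same lean would show itself. Section 9.0 names no analysis of fibrosis beyond general descriptive summaries, so the reading procedure is the main safeguard for any statement that fibrosis improved. At stake are that statement, the reported number of complete as against partial remissions, and any partial remission that depends on the marrow item.

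**Working it through.** **Step 1. Where the marrow reading enters the response categories (Section 6.0).**

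| Category | Marrow item? |
|---|---|
| Complete remission | Yes: cellularity, blasts, fibrosis grade |
| Partial remission, first route | No: blood and clinical items only |
| Partial remission, second route | Yes: same marrow item, lower blood thresholds |
| Clinical improvement | No: anemia, spleen or symptoms |
| Progressive disease | Blasts of 20% or more only |

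**Step 2. Can a misread change responder status?**

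(a) *A patient meets everything for complete remission except marrow.* The first partial-remission route has the same blood thresholds and the same clinical items, and its clinical line ends by opening the alternative: "Clinical: Resolution of disease symptoms; spleen and liver not palpable; no evidence of EMH or". The patient is therefore already a partial remission. A misread moves the patient between the two remission categories and leaves the response rate unchanged.

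(b) *A patient is a partial remission by the second route.* Symptoms have resolved and neither spleen nor liver can be felt. Section 4.0 requires enlargement of the spleen or liver of at least 5 cm at entry. If the marrow item were lost, the patient would usually still qualify as clinical improvement, defined as "The achievement of anemia, spleen or symptoms response without progressive disease or increase in severity of anemia, thrombocytopenia, or neutropenia". Exceptions are narrow: a patient barred by worsening blood counts, or one without a qualifying spleen or symptom response. Marrow blasts near 20% are a further narrow case, through the progression criterion.

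The likely effect on the primary response rate is thus at or near zero.

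**Step 3. The design figures.** Inputs from Section 9.0: null rate 18%, target 35%, stop if 3 or fewer of 16 respond, success if 11 or more of 40 respond. Let X1 ~ Bin(16, p) and X2 ~ Bin(24, p).

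- Early termination at 18%: P(X1 ≤ 3) = 0.678 (stated 68%).
- Expected sample size: 16 + (1 − 0.678) × 24 = 23.7 (stated 23.7).
- Probability of success: sum over x = 4 to 16 of P(X1 = x) × P(X2 ≥ 11 − x). This gives 0.073 at 18% (stated 7%) and 0.802 at 35% (stated 80%).

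The plan's figures are reproduced to the rounding it uses. For scale only: if misreads did raise a true rate of 18% by 1, 2.5 or 5 points, the chance of declaring success would be 9.9%, 14.7% or 25.0% instead of 7.3%. Step 2 gives no reason to expect shifts of that kind.

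**Step 4. Size of the effect on fibrosis.** The documents give no rate of reader bias. Assume that knowing the order moves 10-20% of pairs one grade towards improvement.

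- Trial stops after stage 1: 16 × 0.10 = 1.6 to 16 × 0.20 = 3.2 pairs, about 2-3.
- Trial runs to the end: 40 × 0.10 = 4 to 40 × 0.20 = 8 pairs.

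Both ranges assume that every patient has a complete pair. Patients who leave before the marrow due after 4 cycles lower them. A shifted pair is a false improvement only if the true grade did not change: a true one-grade worsening would read as stable, and a true improvement would be counted anyway. The ranges are therefore ceilings under the assumption.

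**The case against.** The strongest reply is that the plan is silent, not wrong. A reader might infer from the single sitting that the slides are viewed side by side by someone who knows their order. The text does not say so. It is compatible with coded slides, and central review in one sitting is itself a bias control. This stands, and the point has to be that masking is not required. The gap remains, because an unmasked read would meet the plan as written.

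A second reply is that little depends on these readings. Fibrosis is exploratory, and no test or decision rule uses the split between complete and partial remission. Response rate, time to response and duration of response all pool the three response categories. This also stands, and it keeps the point minor. A reader might go further and infer that the primary result or the two-stage rule is biased; the response definitions do not support that.

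A third reply is that the reading note belongs to a published consensus set of criteria that the plan adopts by name, and that rewriting it would blur which standard was applied. That is fair, and it is met by placing the masking rule in a separate procedure.

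Finally, masking is neither complete nor free. Marked histologic change can reveal the order. Once the code is broken after the first pair, the baseline slide is known when a later optional marrow is read. The first limit cannot be avoided. The second is handled by recoding.

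**Conclusion.** The concern holds in a limited form. The plan specifies a paired central read in one sitting and does not require masking to slide order or clinical response. In an uncontrolled trial this exposes the exploratory fibrosis change, the split between complete and partial remission, and marrow-route partial remission to expectation bias. The primary response rate is essentially unaffected, and every Simon design figure stands.

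The size is unknown. The figures of about 2-3 of 16 pairs, or at most 4-8 of 40, rest wholly on the assumed 10-20% one-grade shift and on complete pairs. They should not be read as an estimate of what will happen. The plan's own 68% chance of stopping at 16 patients when the true rate is 18% makes the smaller range the more relevant one if the drug has little activity. This is a worthwhile small improvement, not a threat to the trial's main conclusion.

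**What to change.** Leave the consensus criteria and the single sitting as they are, and add a short reading procedure, for example:

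> For each patient, baseline and post-treatment marrow slides are coded and placed in random order. The central reviewer grades them at one sitting, masked to slide date and clinical response; patient age is supplied so that cellularity can be judged. Someone other than the reviewer holds the code, which is broken only after the grades are recorded. When a later marrow is taken, its slides and the baseline slides are recoded and read in the same way. These grades are used for the marrow criteria of CR and PR and for the summary of fibrosis change.

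The cost is relabelling slides that already go to central review and naming a code-holder. The scheduled pair needs no extra biopsy, reader or reading. Each later optional marrow adds one re-read of the baseline slide. The bias is reduced rather than removed, because a marked change can give the order away. Sample size, stopping rules and patient care are untouched.

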The disease generally occurs in adults, with the median age of 65 years. In 40% of the patients, constitutional symptoms are present, including fever, weight loss, nocturnal sweating, pruritus, and bone pain. Splenomegaly is present in 85% of the patients at diagnosis and is massive in 10%. Hematologic disease features include anemia in 50% to 70% at diagnosis and 25% will have severe anemia with hemoglobin level  $< 8.0$  g/dL. Approximately half of the patients present with an elevated white cell count (WBC), 28% with thrombocytosis (platelet count  $> 500 \times 10^9/L$ ), and 37% with thrombocytopenia (platelet count  $< 150 \times 10^9/L$ ). Circulating blast cells are present in one-third of the patients.

Complications of MF are varied. Thrombotic obliteration of intrahepatic veins and splenomegaly may lead to portal hypertension; severe cases may be associated with ascites and/or variceal bleeding. Left upper quadrant pain may herald splenic infarction; episodes are usually self-limited and may persist for several days. Supportive care measures such as analgesics and hydration are usually sufficient; refractory cases may require splenectomy or irradiation. Extramedullary hematopoiesis (EMH) may occur in locations other than the liver or spleen; involvement of such sites may be managed by low-dose irradiation. Liver involvement is associated with increased levels of plasma alkaline phosphatase. Clinical manifestations of EMH include cardiac tamponade, papular skin nodules, pleural effusions, and spinal cord compression.

Autoimmune phenomena have been observed, including Coomb's positive autoimmune hemolytic anemia, nephrotic syndrome, antinuclear antibodies, rheumatoid factor, and lupus-type anticoagulant. Postulated etiologies include clonality of the lymphoid population or activation by abnormal monocyte-macrophage interaction with the immune system.

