## 4.0 PATIENT ELIGIBILITY CRITERIA

### Inclusion criteria

1. Diagnosis of MF (either primary or post essential thrombocythemia/polycythemia vera) requiring therapy, including those previously treated and relapsed or refractory, or if newly diagnosed, with intermediate-1 or -2 or high risk according to International Prognostic Scoring System (IPSS).
2. Previously treated with ruxolitinib (unless not a good candidate for ruxolitinib therapy in the judgment of treating physician)^
3. Palpable splenomegaly or hepatomegaly of more than or equal to 5 cm below left or right, respectively, costal margin on physical exam
4. Understanding and voluntary signing an IRB-approved informed consent form.
5. No prior history of immune check point modulator therapy
6. Age  $\geq$  18 years at the time of signing the informed consent.
7. Disease-free of other malignancies.
8. ECOG performance status 0 to 2.
9. Negative pregnancy test in females of childbearing potential (FCBP)† Male patients with female partners of child-bearing potential and female patients of childbearing potential are required to use two forms of acceptable contraception, including one barrier method, during their participation in the study and for 23 weeks (for females) or 31 weeks (for males) following the last dose of study medication. Acceptable forms of contraception include 1 highly effective method such as an intrauterine device (IUD), hormonal (birth control pills, injections, or implants), tubal ligation, or partner's vasectomy and at least 1 additional approved barrier method such as a latex condom, diaphragm, or cervical cap plus spermicide. Female patients of childbearing potential must not be breast-feeding or planning to breast feed and must have a negative pregnancy test within 24 hours before first study treatment.
10. Adequate organ function as demonstrated by the following:
  - Direct bilirubin  $\leq$  1.5 x upper limit of normal (ULN)
  - Serum creatinine  $\leq$  1.5 x ULN
  - AST (SGOT) and ALT (SGPT)  $\leq$  2.5 x ULN (unless considered to be related to MF or patient has known history of Gilberts, in which case it must be  $\leq$  5 x ULN)

---

^ Must be documented in medical records (e.g. patient with grade 3 or 4 thrombocytopenia, or severe PRBC transfusion dependency)

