**Table 8.b. Operating characteristics for toxicity monitoring**

True toxicity rate	Prob(stop the trial early)	Average sample size
0.1	0.0006	40
0.2	0.021	39
0.3	0.186	36
0.4	0.583	27
0.5	0.905	17

Summary statistics will be provided for continuous variables. Frequency tables will be used to summarize categorical variables. The objective response rate (ORR) will be estimated along with the exact 95% confidence interval. Data from all subjects who receive any study drug will be included in the safety analyses. The severity of the toxicities will be graded according to the NCI CTCAE v4.03 whenever possible. We will follow standard reporting guidelines for adverse

events. Safety data will be summarized by category, severity and frequency. The proportion of patients with AEs will be estimated, along with the Bayesian 95% credible intervals.

**Duration of response:** Duration of response is defined as the date at which the subject's objective status is first noted to be a CR, PR or CI to the date of progression (no longer meeting criteria for either CR, PR or CI) is documented (if one has occurred). Patients who continue to respond as of the data cut-off date will be censored as of the date of their last assessment documenting continued response.

**Time to response:** The time to response is defined as the time from study registration to the first date at which the subject's objective status was classified as a response (CR, PR or CI). In subjects who do not achieve a response, time to response will be censored at the subject's last evaluation date.

The distribution for each of these event-time variables (duration of response and time to response) will be estimated by Kaplan-Meier curves.

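### The platelet floor for clinical improvement, a component of the primary endpoint, is written as 25 000 × 10^9/L, which no patient can meet; the intended value is not stated

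*Combined protocol and SAP*

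**What the plan says.** Section 9.0 sets the primary endpoint as ORR after 8 doses, "defined as CR (complete remission) + PR (partial remission) + CI (clinical improvement"). Section 6.0 defines CI as an anemia, spleen or symptoms response, subject to conditions in a footnote. One condition is that "assignment to CI requires a minimum platelet count of ≥25 000 × 10(9)/L", together with an "absolute neutrophil count of ≥0.5 × 10(9)/L".

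The other platelet criteria in section 6.0 use the same unit:

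- CR, and the first PR route, need at least 100 × 10^9/L.
- The marrow-based PR route needs at least 50 but less than 100 × 10^9/L.
- All of these are bounded above by the upper normal limit: "and <UNL; <2% immature myeloid cells".

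The CI definition is used again in two places. Relapse in section 6.0 includes "No longer meeting criteria for at least CI after achieving CR, PR, or CI". Section 9.0 ends duration of response when the patient is "no longer meeting criteria for either CR, PR or CI".

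**The concern.** A floor of 25 000 × 10^9/L is not a possible platelet count. It also reverses the ordering of the response categories, because CI would need far more platelets than CR or PR permit. The neutrophil floor in the same sentence, in the same notation, is on a sensible scale, so the problem is confined to the platelet figure. No other part of the document states a platelet floor for CI.

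Taken literally, CI could never be assigned and the primary endpoint would count only CR and PR. If instead assessors treat the figure as a slip, each must decide what was meant. One may apply 25 × 10^9/L, while another may ignore a floor that is plainly impossible. Those are different rules for patients with very low counts.

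Such patients can enter. Section 4.0 sets no platelet minimum, and its footnote on suitability for ruxolitinib gives as an example a "patient with grade 3 or 4 thrombocytopenia, or severe PRBC transfusion dependency". The CI footnote also bars a 2-grade decline in platelets from baseline, but that does not replace an absolute floor: a patient who starts very low has little or no room to fall two grades.

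The go/no-go rules turn on single responses: 3 versus 4 of 16 at stage 1, and 10 versus 11 of 40 at the end.

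**Working it through.** **Inputs**

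- CI platelet floor as written: 25 000 × 10^9/L (section 6.0, CI footnote).
- CR floor: 100 × 10^9/L. Lower bound of the marrow-based PR route: 50 × 10^9/L (section 6.0).
- Thrombocytosis: above 500 × 10^9/L (section 2.1, where the passage reads "28% with thrombocytosis (platelet count").
- Per-microlitre notation elsewhere: 10,000/µL (Concomitant Therapy section).
- Design: null rate 18%, target 35%; stop if 3 or fewer of 16 respond, success if 11 or more of 40 respond (section 9.0).

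**Step 1. Convert the floor as written.** With 1 L = 10^6 µL:

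25 000 × 10^9/L = 2.5 × 10^13/L; 2.5 × 10^13 ÷ 10^6 = 25,000,000/µL.

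**Step 2. Compare with the document's other platelet levels.**

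| Comparator (× 10^9/L) | Ratio |
|---|---|
| CR floor, 100 | 25 000 ÷ 100 = 250 |
| Marrow-based PR lower bound, 50 | 25 000 ÷ 50 = 500 |
| Thrombocytosis level, 500 | 25 000 ÷ 500 = 50 |

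**Step 3. Test the unit-slip explanation.** Read as a per-microlitre number, 25 000/µL × 10^6 µL/L = 25 × 10^9/L. That is 0.25 of the CR floor and 0.5 of the marrow-based PR lower bound, so the floors would be ordered CI 25, marrow-based PR 50, CR and first-route PR 100. The protocol does use per-microlitre platelet counts elsewhere (10,000/µL = 10 × 10^9/L), so a mixture of units is plausible. The value 25 × 10^9/L itself appears nowhere in the document.

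**Step 4. Check whether the design figures are affected.** With b the binomial probability:

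- Early termination = Σ b(x; 16, p) over x = 0 to 3.
- Expected N = 16 + (1 − early termination) × 24.
- P(success) = Σ b(x; 16, p) × P(Bin(24, p) ≥ 11 − x) over x = 4 to 16.

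| Quantity | Recomputed | Stated |
|---|---|---|
| Early termination, p = 0.18 | 0.678 | 68% |
| Expected N, p = 0.18 | 16 + 0.322 × 24 = 23.7 | 23.7 |
| P(success), p = 0.18 | 0.073 | 7% |
| P(success), p = 0.35 | 0.802 | 80% |

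These agree to the precision stated (the 7% only when rounded to a whole percent), and none depends on the footnote. The defect lies in what counts as a response, not in the design arithmetic.

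**The case against.** The strongest reply is that this is a unit typo with no demonstrated effect. The literal reading excludes everyone from CI, so nobody could apply it unnoticed, and the only workable numerical reading offered is 25 × 10^9/L. Section 9.0 also says that responses are categorized by the revised IWG-MRT/ELN consensus criteria, and the reference list gives the citation, so an assessor has a place to resolve the figure. The ratios measure the size of the slip rather than any change in ORR. The document does not say how many patients would have counts near any floor. Finally, the footnote states the floor for assigning CI; that it also governs keeping a response is an inference.

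Much of this stands as a limit on weight. Literal enforcement is unlikely, and no misclassified patient can be identified from the document. It does not remove the defect. The protocol writes out its own criterion rather than relying on the citation, and the written criterion is wrong. Ignoring the floor altogether is a second practical reading, so the meaning is not settled. On the natural reading, the relapse and duration rules refer back to the CI criteria, so they inherit the ambiguity, although this is the same error and not a separate one.

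**Conclusion.** The criterion is wrong as written and should be fixed. The stated floor is 25 million per microlitre, 250 times the CR floor, and it sits inside the primary endpoint. Followed literally, it removes CI from ORR.

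No effect on the chance of success is claimed: the document gives no expected share of responses that would be CI, and assessors would probably not enforce the figure. That the error lies in the text follows from the protocol's own thresholds. That the intended value is 25 × 10^9/L is an inference from units only.

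**What to change.** Correct the CI footnote in section 6.0 so that number and unit agree. Unit consistency points to 25 × 10^9/L (25,000/µL), but the sponsor should confirm the value against the consensus response criteria it cites before amending. Then derive CI, relapse and duration of response from the corrected floor, and recheck any CI calls already made.

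The cost is a one-line protocol correction and that recheck. No patients, visits or tests are added, and the sample size and stopping rules are unchanged.
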